ClinicalTrials.gov ID: NCT04173741

Brief Title: Is There Any Correlation Between Respiratory Variation Ratios of Internal Jugular Vein and Inferior Vena Cava?

Official Title: A Correlation Study in the Intensive Care Unit Between the Respiratory Variation Ratios of Internal Jugular Vein and Inferior Vena Cava Before and After Passive Leg Raise

Date: 01 December 2019

Study Protocol: For this prospective observational study, we took consent of the Hacettepe University Non-Interventional Clinical Researches Ethics Board (GO 17/427-34). All adult (aged 18 or older) mechanically ventilated patients admitted consecutively to Hacettepe University Hospital Anesthesiology Intensive Care Unit were screened for study eligibility. Patients with infection or surgical sutures in the site of measurement areas, intraabdominal hypertension, severe aortic regurgitation or lower extremity amputation history were excluded from the study. For eligible patients, we took informed consent from patients themselves or from their guardians.

Ultrasonography (USG) measurements were done separately by 3 different physicians; one senior anesthesiology resident, one critical care medicine fellow (who joined two hands-on USG training before) and one professor in anesthesiology and critical care (USG trainer with more than 1000 USG measurement experience). Anesthesiology resident took 2 hours of didactic lecture about IJV and IVC ultrasonography and performed 5 practices under supervision of the instructor before starting the USG measurements for this study. Physicians neither watched each other's measurements nor were informed about each other's measurement values.

The diameters of inferior vena cava (IVC) and internal jugular vein (IJV) were measured in two different positions. First measurements of IVC and IJV were done in supine position and second ones were done after passive leg raise (PLR) maneuver. For the passive leg raise maneuver legs were elevated 45 degrees. USG measurements were performed 1-3 minutes after PLR.

Philips CX50 Ultrasonography Machine (Philips Ultrasound, Andover, MA, USA) was used for all of the measurements. IJV diameter was measured in the short axis by using linear probe (12-5 MHz) and M-mode. IJV visualized in the junction of cricothyroid membrane level and midclavicular line. Maximum and minimum diameter values were measured in the M mode.

IVC was visualized in the subxiphoid long axis by using convex probe (5-1 MHz). Maximum and minimum diameters of IVC was measured 2 cm caudally to the junction of hepatic vein in M-mode.

Distensibility (maximum diameter – minimum diameter / minimum diameter) and collapsibility (maximum diameter – minimum diameter / maximum diameter) indices were calculated after USG measurements were done.

Oxygen saturation, heart rate and blood pressure levels were recorded before and after measurements. We also recorded age, gender, weight, height, body mass index, causes of admission, comorbidities, ventilator settings, vasoactive and diuretic medications, fluid intake and output volumes, Acute Physiology and Chronic Health Evaluation (APACHE) II and Sequential Organ Failure Assessment (SOFA) scores in the day of admission, Acute Physiology Score (APS) and SOFA scores on the day of measurement and length of stay in intensive care unit.

Statistical Analysis: We calculated that 44 patients should be included in this study to investigate correlation between IVC and IJV measurements with 0.4 effect size, 0.05 Alfa error and 0.80 power by using G*Power 3.1 software. A total of 46 patients in Hacettepe University Hospital Anesthesiology Intensive Care Unit were required to enroll into this study to reach that number of patients.

We used “IBM SPSS Statistics 23” for statistical analysis. Distribution of the data was analyzed with Kolmogorov- Smirnov Test. For normally distributed data we calculated mean and standard deviation, for the others we calculated median and percentile [5-95] values. We used Spearman correlation test for correlation analysis of measurements of different physicians. We used Spearman correlation test to analyze the correlations between IVC and IJV measurements. Subgroups were listed as patients on vasopressors vs no vasopressors, patients on vasodilators vs no vasodilators, patients on diuretics vs no diuretics, patients with 20mmHg and over vs <20 mm Hg plateau pressure levels, patients with 15mmHg and over vs <15 mm Hg driving pressure levels, patients with over 5mmHg PEEP levels vs PEEP<5 mm Hg, patients with surgical cause of admission vs others, patients who were stayed 1 minute in passive leg raise position vs patients who were stayed 3 minutes in passive leg raise position. A p value less than .05 was considered statistically significant.

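### The 80% power claimed for 44 patients does not belong to the planned Spearman test, which has about 73–77% power at a correlation of 0.4 (two-sided, bivariate normal data)

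*Combined protocol and SAP*

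**What the plan says.** The whole sample size justification is in the Statistical Analysis section: "We calculated that 44 patients should be included in this study to investigate correlation between IVC and IJV measurements with 0.4 effect size", with "0.05 Alfa error and 0.80 power by using G*Power 3.1 software". The plan is to enrol 46 patients, who "were required to enroll into this study to reach that number of patients"; the two extra patients serve only to secure 44.

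The same section fixes the test: "We used Spearman correlation test to analyze the correlations between IVC and IJV measurements". It also provides for non-normal data: "Distribution of the data was analyzed with Kolmogorov- Smirnov Test", with medians and percentiles where normality fails.

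Three things are not stated: which G*Power routine was run, whether the test is one- or two-sided (only a threshold of p < .05 is given), and whether 0.4 is a Pearson or a Spearman coefficient. No allowance for a rank test is described.

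**The concern.** A power figure applies to one test against one alternative. With normal data, Spearman's test is somewhat less powerful than Pearson's at the same underlying correlation. A sample size taken from a non-rank routine therefore overstates the power of the Spearman analysis unless something is added for it.

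This is the plan's only sample size justification, and it concerns the question in the study's title. If true power is below 80%, a non-significant IVC–IJV correlation is weaker evidence of no association than the plan implies. The type I error is not in question.

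**Working it through.** **Inputs from the Statistical Analysis section:** n = 44 analysed (46 enrolled), effect size 0.4, alpha 0.05, power 0.80, Spearman test.

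**Assumptions, not in the documents:** two-sided test; bivariate normal data, except in step 4.

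**1. Reproduce 44.** For the two-sided point-biserial model, use the noncentral t distribution with df = N − 2 and noncentrality √(N·ρ²/(1 − ρ²)). Here ρ²/(1 − ρ²) = 0.16/0.84 = 0.1905.

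- N = 43: √(43 × 0.1905) = 2.862, power 0.798.
- N = 44: √(44 × 0.1905) = 2.895, power 0.807.

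So 44 is the smallest N reaching 0.80. A one-predictor regression F test with λ = N·ρ²/(1 − ρ²) gives identical numbers. Other routines do not return 44:

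| Routine | Two-sided N | One-sided N |
|---|---|---|
| Point-biserial / one-predictor regression | 44 | 34 |
| Exact bivariate normal (Pearson) | 46 | 37 |
| Fisher z | 47 | 38 |

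The routine is an inference, but two-sided is clearly the likelier reading, and none of these routines is for a rank test. The exact Pearson test at n = 44 has power 0.784.

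**2. Put 0.4 on both scales.** Under bivariate normality, rank ρ = (6/π)·arcsin(r/2).

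- Pearson 0.4 corresponds to rank (6/π)·arcsin(0.2) = 0.385.
- Rank 0.4 corresponds to Pearson 2·sin(π × 0.4/6) = 0.416.

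**3. Power of Spearman's test.** Simulation with 200,000 replicates per setting, t approximation, two-sided 0.05 (simulation standard error about 0.001):

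| n | 0.4 is Pearson | 0.4 is rank |
|---|---|---|
| 44 | 0.731 | 0.768 |
| 46 | 0.752 | 0.788 |
| 48 | 0.771 | 0.806 |
| 52 | 0.804 | 0.839 |

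With ρ = 0 and n = 44 the test rejects in 0.050 of replicates, so alpha holds. At n = 44, power is 0.798 at Pearson 0.43 (rank 0.414) and 0.807 at 0.435 (rank 0.419). The correlation detectable with 80% power is therefore about 0.43, or about 0.415 on the rank scale.

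**4. Sensitivity to skew.** Suppose 0.4 is a Pearson correlation between lognormal variables with a normal copula. The copula correlation is then ln(1 + 0.4·CV²)/ln(1 + CV²). For CV 53%, CV² = 0.281 and the result is 0.430. Spearman power at n = 44:

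| CV | 20% | 31% | 42% | 53% | 66% |
|---|---|---|---|---|---|
| Power | 0.74 | 0.76 | 0.78 | 0.80 | 0.83 |

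The documents give no SD or distribution, so the applicable CV is unknown. If 0.4 is a rank correlation, skew in the margins changes nothing, because ranks are unaffected by monotone transformation; 0.768 then needs only a normal dependence structure.

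**5. Sensitivity to sidedness.** One-sided Spearman power at n = 44 would be 0.83 (Pearson 0.4) or 0.85 (rank 0.4).

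**6. Precision.** For ρ = 0.4 and n = 44, Fisher z with variance 1.06/41 gives a 95% interval of 0.108 to 0.628; with variance (1 + ρ²/2)/41 it gives 0.105 to 0.630.

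**The case against.** The number 44 is not a miscalculation: a standard two-sided routine returns it exactly. This stands; the mismatch is between the sizing model and the planned test.

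Not all of the shortfall comes from ranking. The exact Pearson test at n = 44 already has 0.784, so 0.807 − 0.784 = 2.3 points come from the inferred routine. This also stands. On the rank reading one might then charge ranking with only 0.784 − 0.768 = 1.6 points, but that comparison changes the alternative as well as the test. At the same underlying correlation of 0.416, Pearson's test has 0.818 against Spearman's 0.768, a cost of 5 points.

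The 73% end needs 0.4 to be a Pearson coefficient and the data to be normal, while the plan names only Spearman and does not assume normality. This is fair. The rank reading is also natural because distensibility D and collapsibility C satisfy D = C/(1 − C), an increasing function, so the IVC–IJV Spearman correlation is the same for either index. On that reading the figure is 77%, still about 3 points short, and 79% with all 46 patients.

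A one-sided test, or strong skew with a Pearson 0.4, would restore 80%. Both are possible. But no one-sided routine tried returns 44, and the skew route needs a CV of about 53% or more.

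Finally, the practical effect is small. That limits the weight of the point but does not make the stated power correct.

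**Conclusion.** The point holds. Under the likeliest reading (two-sided, normal dependence), 44 patients give Spearman's test about 77% power if 0.4 is a rank correlation and about 73% if it is a Pearson correlation between normal variables. Against the stated 80% that is 3 to 7 points less, and a 23–27% chance of missing a true 0.4. Analysing all 46 patients gives 75–79%. For scale, 80% would need about 48 or 52 analysed patients respectively.

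Confidence in the calculation is high. It is conditional on the sidedness, the scale of 0.4 and the distribution, none of which the plan states. The consequence is modest: the plan's power claim is slightly too favourable, and alpha is unaffected.

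**What to change.** Replace the statement of 80% power at 0.4 with wording such as: *Assuming bivariate normality, 44 analysable patients give about 73% (Pearson 0.4) to 77% (Spearman 0.4) power for a two-sided Spearman test at alpha 0.05, and 80% power at an underlying correlation of about 0.43 (rank correlation about 0.415).*

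Alongside it, state the G*Power routine, confirm that the test is two-sided, and say which coefficient 0.4 refers to. If it is a Spearman correlation, only the 77% figure is needed, and it does not depend on skew in the indices. If the authors in fact intended a one-sided test, they should say so and use the one-sided figures in step 5 instead.

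Report rho with its 95% confidence interval (about 0.11 to 0.63 if rho is 0.4 with 44 patients), so that a non-significant result is read from the range of correlations it leaves open.

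The cost is wording only. The stated power becomes less favourable by about 3 points on the rank reading or 7 on the Pearson reading. The test and the number of patients stay as they are.

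### The three physicians' readings are compared only by Spearman correlation, which cannot show whether the operators obtain the same values

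*Combined protocol and SAP*

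**What the plan says.** The Study Protocol section of the combined protocol and SAP states: "Ultrasonography (USG) measurements were done separately by 3 different physicians". Their experience differs widely. The resident had a two-hour lecture and "performed 5 practices under supervision of the instructor before starting the USG measurements for this study", the fellow had attended two hands-on trainings, and the professor is a trainer with more than 1000 measurements. They worked blind to each other: "Physicians neither watched each other's measurements nor were informed about each other's measurement values".

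The same section defines distensibility as (max − min)/min and collapsibility as (max − min)/max. After the leg raise, "USG measurements were performed 1-3 minutes after PLR".

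On comparing the physicians, the Statistical Analysis section has one sentence: "We used Spearman correlation test for correlation analysis of measurements of different physicians". The only decision criterion is general: "A p value less than .05 was considered statistically significant". The plan contains no mean difference between operators, paired test, limits of agreement, intraclass correlation or measurement-error estimate. It does not state the aim of the operator comparison, which measurements enter it, or whose readings feed the IVC-IJV correlation.

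**The concern.** Two people scanning the same vein in the same patient should produce correlated readings, so rejecting rho = 0 says little. The useful question is whether a newly trained operator obtains the same values as an expert. A typical failure would be systematic, for example a different caliper placement or a minimum diameter consistently read low. Spearman's rho works on ranks, and adding a constant to one reader's diameters, or multiplying them by a positive factor, leaves the ranks unchanged.

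For the indices the position is more nuanced. A purely proportional error cancels in both ratios, so nothing is missed there. An offset in both diameters, or in the minimum alone, does not cancel. It shifts the level of the index and barely disturbs the ranking.

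What is at stake is the inter-operator result. A high rho could be read as evidence that the operators are interchangeable, and it cannot carry that meaning.

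**Working it through.** **Inputs from the documents.** Three mutually blinded operators; Spearman as the only comparison; significance at .05; 44 patients required; the two index formulas. Everything about measurement error below is assumed.

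**The plan's own figure.** The sample size of 44 (effect size 0.4, alpha 0.05, power 0.80) reproduces under the point-biserial correlation model, two-sided: noncentrality √44 × 0.4/√(1 − 0.16) = 2.895, df 42, power 0.807. It concerns the IVC-IJV correlation and is not in dispute here.

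**Step 1. Diameters.** Assume a between-patient SD of 1 and error SD of 1/3, so single-reader reliability is 1/(1 + 1/9) = 0.90. Offset the second reader by d SDs. For a pair, the absolute-agreement ICC is 1/(1 + 1/9 + d²/2). Rho is from 200,000 simulated pairs.

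| Offset d (SD) | Spearman rho | Absolute-agreement ICC |
|---|---|---|
| 0 | 0.89 | 1/1.111 = 0.90 |
| 0.5 | 0.89 | 1/1.236 = 0.81 |
| 1 | 0.89 | 1/1.611 = 0.62 |
| 2 | 0.89 | 1/3.111 = 0.32 |

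**Step 2. Indices, one patient.** Assume maximum 20 and minimum 16.
- No error: distensibility 4/16 = 0.25, collapsibility 4/20 = 0.20.
- Both diameters multiplied by 1.5: 6/24 = 0.25 and 6/30 = 0.20, unchanged.
- Both diameters +2: 4/18 = 0.22 and 4/22 = 0.18.
- Minimum −1: 5/15 = 0.33 and 5/20 = 0.25.

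**Step 3. IVC distensibility, simulated.** Assume maximum diameter with mean 18 and SD 4 mm; distensibility log-normal with median 0.18 and log-SD 0.6; independent error of SD 0.3 mm on each diameter; about 200,000 pairs. Pairs with maximum not above minimum (at most 0.5%) are excluded.

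| Error in second reader | rho | ICC | Median, reader A vs B |
|---|---|---|---|
| none | 0.90 | 0.94 | 0.18 vs 0.18 |
| both diameters × 1.5 | 0.90 | 0.94 | 0.18 vs 0.18 |
| both +2 mm | 0.89 | 0.90 | 0.18 vs 0.16 |
| both +5 mm | 0.89 | 0.77 | 0.18 vs 0.14 |
| minimum −1 mm | 0.88 | 0.78 | 0.18 vs 0.27 |

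Doubling the random error to 0.6 mm lowers rho to 0.70, and adding a 5 mm offset to that leaves it at 0.70. Rho responds to random error and hardly at all to bias. For the IJV (assumed maximum 11, SD 3 mm, error 0.3 mm), a minimum read 1 mm low takes rho from 0.77 to 0.74 but the ICC from 0.85 to 0.54.

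**Step 4. Significance as a criterion.** At n = 44, the smallest significant correlation is t/√(42 + t²) with t = 2.018, that is 0.297. The simulated chance of p < .05 is 46%, 91% and 99% at single-reader reliability 0.3, 0.5 and 0.6. Poor reliability would often give a significant result.

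**Step 5. Can 44 patients estimate bias?** With reliability R, the error variance is (1 − R)/R in units of the between-patient variance. The 95% CI half-width for a pairwise mean difference is t(43) × √(2(1 − R)/R)/√44. At R = 0.9 this is 2.017 × 0.471/6.633 = 0.14 SD. It widens to 0.28, 0.43 and 0.66 SD at R = 0.7, 0.5 and 0.3.

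**The case against.** - **The plan promises only correlation.** The titles and the sample size concern the IVC-IJV correlation, and agreement or interchangeability is never claimed. This stands: the point is a gap in a secondary analysis, not a contradiction. The gap remains, because the blinded three-operator design can answer a question that the named statistic cannot.
- **The main result is hardly affected.** With the assumptions above and an assumed latent IVC-IJV correlation of 0.4, the IVC-IJV rho is 0.319 without bias, 0.318 and 0.317 with both IVC diameters 2 and 5 mm high, and 0.314 with the IVC minimum 1 mm low. This stands if one reader's data are used; pooling readers could differ, and the documents do not say which is done.
- **Some illustrated biases are large.** True of 5 mm and of 2 SD. Milder errors do less: the index ICC is 0.93 with both diameters 1 mm high and 0.89 with the minimum 0.5 mm low. No bias is shown to exist. But 1 mm on the minimum alone raises the median index by about half (0.27/0.18 = 1.5) with rho almost unchanged.
- **The plan does not say that the operator comparison rests on the p value.** Correct as far as it goes: the .05 rule is general. No other criterion is given, however.
- **The sample is less informative at lower reliability.** True, as step 5 shows. It also assumes that all 44 patients are read by all three physicians, which is not expressly stated. A wide interval would still report the uncertainty honestly.

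**Conclusion.** The concern holds and should be fixed. As planned, the comparison can establish association between the physicians' readings and can reveal random imprecision. It cannot show whether the three physicians obtain the same diameters or indices. Under the assumptions used, rho stays within about 0.02 of its unbiased value for IVC distensibility while the ICC drops by up to 0.17 (0.94 to 0.77). For diameters, rho does not move while the ICC falls to 0.62 at a one-SD offset.

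That rank correlation is unchanged by a shift or rescaling of the diameters needs no assumption. The sizes rest on assumed error and bias, since the documents give neither. The IVC-IJV correlation and its sample size are not called into question by this point.

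**What to change.** Add a short paragraph to the Statistical Analysis section:

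- For each pair of physicians, report the Bland-Altman mean difference with 95% CI and the 95% limits of agreement. Report a two-way absolute-agreement ICC with 95% CI. Spearman's rho may stay as a descriptive figure.
- Do this for the maximum and minimum diameters and both indices of each vein. Log-transform skewed indices, and state beforehand how an index of zero is handled, since its log is undefined.
- Make the supine readings the main comparison. Report agreement after the leg raise second, and interpret it in light of the 1-3 minute window, because timing may mix with operator differences.
- Base any inter-operator conclusion on the pairwise bias and the ICC interval, not on p < .05 for rho = 0. With three operators, give the pairwise bias more weight than the ICC's operator-variance component.

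**Cost.** No new scans: the planned between-physician correlation already needs paired readings, and SPSS 23 computes the ICC. Reported in full, this is 3 pairs × 4 measures × 2 veins × 2 positions = 48 mean differences. Because collapsibility equals distensibility/(1 + distensibility), the second index adds little, so the main table can carry the supine diameters and one index, with the rest in a supplement. The downsides are that the agreement figures may look less favourable than rho, and that the operator-variance component is imprecise with three operators.
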